## **Introduction (Background and Rationale)**

Renal disease is commonly found in patients undergoing liver transplant evaluation. In the terminal stages of liver disease, approximately 75% of patients develop oligoanuric renal failure. [1] One study of 102 liver allograft recipients revealed 25% experienced renal impairment before transplantation and 67% after transplantation. [2] This study also showed that pre-transplantation renal dysfunction was an independent predictor of postoperative mortality. Numerous factors may affect renal function in the end-stage liver disease patient. Some include hepatorenal syndrome, the complexity of the operation for liver transplantation, and the potential for postoperative graft dysfunction. [3,4] Furthermore, the incidence of short term renal dysfunction can be linked to the pre-transplant model for end stage liver disease (MELD) score. Specifically, elevations in pre-transplant serum creatinine which is one of three factors used to calculate the MELD score for organ allocation are associated with reduction in renal function and are a negative predictive factor for patients with cirrhosis (and after OLT). [4]

Despite extensive knowledge of post operative renal dysfunction in liver transplant recipients, chronic renal failure following liver transplantation remains one of the most challenging complications with chronic renal failure occurring in up to 18-20% of OLT recipients after five years [5,6]. The etiology of altered renal function following OLT is complex, but one of the most important risk factors is the nephrotoxic effects of the therapeutic agents required to guard against rejection, namely long term calcineurin inhibitor usage. [1,7] Tacrolimus (TAC) and cyclosporin (CYA), are known as the calcineurin inhibitors (CNIs). These immunosuppressive drugs are routinely used to help prevent rejection following solid organ transplantation. Along with other advances, these agents have helped most liver transplant centers achieve one year survival rates higher than 85% because of better clinical management. [8] Nephrotoxicity is the most notable adverse effect associated with CNI therapy. CNIs can cause long-term structural and functional changes to the kidney, contributing to the long term problems seen in transplant patients. [9-11] Histologically, striped tubulointerstitial fibrosis, tubular atrophy, and afferent arteriopathy are noted. [9,12-14] CNIs have been reported to elucidate transient reductions in renal plasma flow and glomerular filtration rate that results from acute, reversible renal hypoperfusion with the greatest change in GFR in the first 3-6 months. [15] This continual renal hypoperfusion might explain the structural changes and long term functional deterioration of the pre-glomerular, afferent arterioles and be a critical indicator of future problems.

Therefore, OLT recipients with pre-existing renal impairment or high (renal driven) MELD scores could benefit from alternative immunosuppressive strategies in the immediate and long term post-transplant settings. Immunosuppressive regimens that are calcineurin

sparing, calcineurin free or regimens that add novel agents such as mTOR inhibitors (e.g. everolimus) at specific times following transplant in order to reduce CNI exposure or withdraw them entirely have been suggested and studied on a limited basis. [16-20]

Recently at our center, we completed a pilot trial in 60 adult OLT recipients in which we compared our standard triple immunosuppressive therapy with TAC plus myfortic and a standard of care corticosteroid taper to induction therapy with basiliximab with delayed use of tacrolimus therapy (until post-operative day 7), combined with myfortic and a rapid corticosteroid taper. The delay in tacrolimus therapy in the basiliximab induction group resulted in a mild improvement in renal function by three months following transplant while maintaining adequate immunosuppression to prevent acute rejection. This study was limited in the number of subjects enrolled and suffered from an inability to further reduce CNI exposure and perhaps enhance renal recovery or improvement following OLT. Thus additional CNI sparing agents could benefit these recipient with respect to enhancing renal function over time.

Everolimus is an mTOR inhibitor that is a structural derivative of sirolimus, with a distinct pharmacokinetic profile (shorter half-life and twice a day dosing). Clinical experience showed that a pharmacokinetic interaction of tacrolimus on everolimus may be less than with cyclosporine or even absent, and that the combination of everolimus and tacrolimus was safe and well tolerated with no new safety risks identified. [21, 22]

It has been approved for use in liver transplant recipients in combination with corticosteroids and reduced dose tacrolimus. Approval was based on a large study (n=719) in which delayed everolimus (introduced POD 30) with reduced dose tacrolimus (39% reduction of tacrolimus) showed comparable efficacy (incidence of biopsy proven acute rejection, graft loss or death) and had superior renal function as early as 1 month compared to standard dose tacrolimus. [23] Additionally, several small or retrospective studies have reported the use of everolimus in OLT recipients in combination with CNI reduction or as a CNI withdrawal strategy. [24-26]

Similar to the CNIs, everolimus administration includes trough level therapeutic drug monitoring (TDM). This practice has evolved largely due to the relatively narrow therapeutic window for immunosuppression, the considerable inter- and intraindividual pharmacokinetic variability, as well as the high incidence of drug-drug interactions resulting from hepatic metabolism via cytochrome P450 isoenzyme 3A4 (CYP3A4). Results in adults using therapeutic drug level monitoring of everolimus target an everolimus C-0h blood trough level of 3-8 ng/mL. [27, 28]

Previously, the risk of hepatic artery thrombosis (HAT), leading to an increased rate of patient death within the first 30 days post-transplantation, was identified as a concern after liver transplantation using sirolimus. [29] However, recent results suggest that sirolimus used at low doses or early after the immediate peri-operative period was not associated with HAT. [30] HAT has neither been associated with the use of everolimus. [31] However, the Phase III trial conducted in *de novo* adult whole liver transplantation implemented delayed everolimus administration (POD 30 ± 5 days) to limit the risk of drug induced HAT.

Therefore, based on the available data and experience in OLT recipients and building on our previous UCLA pilot trial design and experience, the potential benefit from the introduction of delayed everolimus and improved renal function related to reduction of calcineurin inhibitors (CNI) over time and enhanced safety profile warrants additional investigation.

Thus, we propose a randomized, prospective investigator initiated study that will compare basiliximab induction, delayed TAC exposure plus MMF and a SOC corticosteroid taper (group 1; n=36), compared to basiliximab induction, delayed TAC exposure plus MMF and a SOC corticosteroid taper with a delayed everolimus facilitated CNI reduction at POD 30 and mycophenolate minimization to further enhance renal function (group 2; n=36) versus control (standard dose TAC plus MMF and standard of care corticosteroid taper; group 3; n=18).

Clearly, the primary objective assesses rate and severity of rejection, allograft loss and death as well as post-operative renal function (measured as estimated GFR). The proposed study will also evaluate the mTOR class effects (e.g., dyslipidemia, impaired wound healing and proteinuria) and in addition, it will monitor closely the potential safety effects of chronic mTOR inhibitor therapy upon infectious complications such as CMV, and HBV and HCV.

## **Purpose**

### Primary Objectives

- To evaluate the evolution of renal function assessed by dialysis independence and time to independence from dialysis.

## Secondary Objectives

- Glomerular Filtration Rate (eGFR); Cockcroft and Gault (MDRD)
- To determine the incidence of confirmed acute rejection episodes in patients undergoing orthotopic liver transplant at 1, 3 and 6 months post-transplant
- To determine the tolerability and adverse event profile of basiliximab, delayed dose tacrolimus, mycophenolate mofetil, SOC corticosteroids and Everolimus during the first six months post-transplant
- To determine the incidence of infectious complications during the first six months post-transplant
- To determine the time to the first episode of acute rejection
- To determine the severity of each acute rejection episode
- To determine the incidence of death and/or graft failure within the first six months post-transplant
- To determine the number of patients requiring full dose CNI rescue therapy
- To determine the mean serum creatinine concentration and eGFR: Cockcroft and Gault (MDRD) at weeks 1, 2, 4, 8, 12, 16, 20 and 24 post OLT
- To monitor CD25 cell count for the first 3 months post-transplant
- Economic analysis to determine cost-effectiveness of induction therapy with IL-2 monoclonal antibody
- Economic analysis to determine cost-effectiveness of delayed therapy with everolimus

## **Efficacy objectives at 1, 2, 3, and 5 months after start of everolimus**

To assess:

- Rate of composite efficacy failure of treated biopsy proven acute rejection (tBPAR), graft loss (GL) or death (D).
- Time to event and severity of tBPAR.
- Incidence and severity of all acute rejection.

To evaluate:

- Renal function over time assessed by mean change in eGFR by the Cockcroft and Gault (MDRD) from the start of everolimus.
- Urinary protein/creatinine ratio at various time points
- Incidence of and time to renal replacement therapy.

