## **PRIMARY ENDPOINTS**

- Assessment of the nephroprotective effects of everolimus in combination with simulect, or simulect alone following OLT at months 2, 3, 4, 5 and 6.

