## **Investigational Treatment**

### **Introduction and maintenance of everolimus**

Everolimus will be introduced at the earliest 1 month after liver transplantation for all patients to minimize the potential risks of wound healing and vascular complications of the graft. At the start of the treatment period (Day 1), patients will receive the first dose of everolimus (1 mg twice daily in 12 hr intervals)

By Day 4, the everolimus dose will be adjusted to achieve targeted C-0h blood trough level between 3-8 ng/mL. All patients will continue to receive everolimus with CNI reduced dose for 6 months. Mycophenolate will be minimized as clinically indicated in subjects (group 2) receiving everolimus and tacrolimus.

The dose of everolimus must be taken twice-daily, 12 hours apart, in the morning and evening dose AFTER tacrolimus administration (everolimus or tacrolimus dose administrations should not be more than 10 minutes apart). The morning or evening everolimus dose should be taken consistently either with or without food as the patient prefers. To prevent alteration of study drug absorption, grapefruit or grapefruit juice are not allowed throughout the study.

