## **Biopsy proven acute rejection and treated biopsy proven acute rejection**

A biopsy proven acute rejection (BPAR) is defined as clinically suspected acute rejection confirmed by biopsy. In all suspected acute rejection episodes, regardless of initiation of anti-rejection treatment, a graft core biopsy will be performed preferably within 24 hours, latest within 48 hours whenever clinically possible. Whenever it is possible, anti-rejection therapy should be postponed until a local histological diagnosis of rejection is confirmed. The liver biopsies will be read by the pathologist according to the Banff classification of liver allograft rejection. The local histo-pathology results will be used for patient treatment and management. A treated biopsy proven acute rejection (tBPAR) will be considered as efficacy event if the local pathologist reading with a RAI score  $\geq 3$  of acute rejection index was applied and consecutive anti-rejection therapy was administered to the patient. These readings will be used to assess the efficacy endpoint at Months 3 and 5 after the start of everolimus based regimen.

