Official Title:

A Study in Adults on Pre-LT Dialysis With Basiliximab, Delayed Tacrolimus (TAC), Mycophenolate (MMF), and Steroids (Group 1) vs. Basiliximab, Delayed TAC, MMF, Steroids, With Everolimus 30 Days Post-LT (Group 2) vs. TAC, MMF, and Steroids (Group 3)

NCT Number:

NCT04104438

Document Date:

September 3, 2020

Statistical Analysis

Continuous variables were expressed as median (range) and were compared using the Mann-Whitney U test. Categorical variables were expressed as a numerical percentage and compared by the Chi-square test or the Fishers Exact Test. Survival curves were generated by the Kaplan-Meier method, and differences in survival rates were analyzed using the Log-Rank test. All tests were two-sided, and the significance level was $p<0.05$. All analyses were performed using IBM® SPSS® Statistics version 26 (IBM Corporation, Armonk, NY).

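### The composite efficacy failure, tBPAR and eGFR-change objectives are timed from the start of everolimus, which only Group 2 has; 54 of 90 subjects have no time zero for them

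*Protocol*

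**What the plan says.** The Protocol's Efficacy objectives section is headed with assessment times of 1, 2, 3 and 5 months counted from the start of everolimus. Under that heading come the rate of the tBPAR, graft loss or death composite, the time to and severity of tBPAR, and "Renal function over time assessed by mean change in eGFR by the Cockcroft and Gault (MDRD) from the start of everolimus". The section defining biopsy-proven and treated biopsy-proven acute rejection repeats the clock with fewer times: "These readings will be used to assess the efficacy endpoint at Months 3 and 5 after the start of everolimus based regimen".

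The Drug Therapy sections list everolimus for Group 2 only. The Introduction agrees, describing that arm as the one "with a delayed everolimus facilitated CNI reduction at POD 30 and mycophenolate minimization to further enhance renal function (group 2; n=36"). The section on introduction and maintenance of everolimus ties the start to a personal date: "At the start of the treatment period (Day 1), patients will receive the first dose of everolimus". It also says "Everolimus will be introduced at the earliest 1 month after liver transplantation for all patients", which does not fit the Group 2-only regimens.

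The Protocol's Statistical analysis section reads TBD. The SAP says that "differences in survival rates were analyzed using the Log-Rank test" and gives no time origin.

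Other objectives run on a different clock. The Secondary Endpoints and Secondary Objectives date rejection (1, 3 and 6 months), death and/or graft failure (6 months) and eGFR level (weeks 1 to 24) from transplant, in every arm.

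**The concern.** A between-arm comparison needs a time zero that every randomised patient has and that does not depend on what happens after randomisation. The start of everolimus meets neither condition. It comes about a month after transplant, in one arm, in those patients who reach it and start the drug. It is also not stated whether a rejection, graft loss or death before that date counts.

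The composite and the change in eGFR appear nowhere else in the Protocol on a transplant clock. Read as written, they describe Group 2 starters only. A change in eGFR after everolimus starts would then have no concurrent control. It could not be separated from the renal course that these patients would have had anyway, in a population that may enter on dialysis.

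**Working it through.** **Inputs.** 90 subjects, allocation 2:2:1, arm sizes 36, 36 and 18 (Protocol, Patient Population). Everolimus in Group 2 only (Protocol, Drug Therapy). Six months' follow-up from transplant (Protocol, Patient Population). eGFR at weeks 1, 2, 4, 8, 12, 16, 20 and 24 (Protocol, Secondary Endpoints).

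**Step 1: the plan's own figure.** 90 × 2/5 = 36, 90 × 2/5 = 36 and 90 × 1/5 = 18. The stated arm sizes are reproduced.

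**Step 2: who has the index date.**
- Not assigned everolimus: 36 + 18 = 54, and 54/90 = 60%.
- Can have the index date: at most 36, and 36/90 = 40%. Each Group 2 patient who never starts lowers this number.

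**Step 3: does any section supply a substitute day for Groups 1 and 3?**

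| Place | Time origin given |
|---|---|
| Protocol, Efficacy objectives | Start of everolimus |
| Protocol, tBPAR definition | Start of everolimus |
| Protocol, Introduction and maintenance of everolimus | Day 1 is the first everolimus dose |
| Protocol, Secondary Endpoints and Objectives | Transplant, but neither the composite nor the eGFR change is listed |
| Protocol, Statistical analysis | None (TBD) |
| SAP | None |

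None does.

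**Step 4: could a nominal day 30 have been meant?** Take a month as 365.25/12 = 30.44 days and count from post-operative day (POD) 30:

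| Months after POD 30 | Day after transplant | Post-transplant month | Nearest planned visit named in the fix | Gap |
|---|---|---|---|---|
| 1 | 30 + 30.4 = 60.4 | 2 | Week 8 (day 56) | 4 days |
| 2 | 30 + 60.9 = 90.9 | 3 | Week 12 (day 84) | 7 days |
| 3 | 30 + 91.3 = 121.3 | 4 | Week 16 (day 112) | 9 days |
| 5 | 30 + 152.2 = 182.2 | 6 | Week 24 (day 168) | 14 days |

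All four months lie on the grid in the Primary Endpoints ("following OLT at months 2, 3, 4, 5 and 6"). A POD 30 landmark is therefore a plausible intention, but no section applies it to Groups 1 and 3.

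**Step 5: is transplant a workable common origin?** The written regimens of Groups 1 and 2 are the same up to POD 30, and Group 3 differs from both from the start. Counting from transplant is therefore valid for all three pairwise comparisons and excludes no randomised patient.

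**The case against.** The strongest reply is that this list is supplementary. It is not among the synopsis primary or secondary endpoints, and the main components are already dated from transplant in all arms. The list does not say that its items are compared between arms, and as a description of Group 2 it needs no index day elsewhere. A POD 30 landmark also fits the grid, and the SAP title speaks of "With Everolimus 30 Days Post-LT (Group 2"). Much of this stands. It limits the gap to the assembled composite, tBPAR on this clock and the eGFR change. It does not close the gap, because nothing labels the list as Group 2 only and POD 30 is never written as the index for the other arms.

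Four stronger readings are tempting, and the documents do not support them:
- **No randomised efficacy comparison is left.** The transplant-dated secondary endpoints provide one.
- **The arms will be analysed on mixed clocks, with only Group 2's first month uncounted.** No section describes such an analysis.
- **Month 5 runs past follow-up.** The regimen adds everolimus by POD 30, which puts month 5 at about day 182 against six months at about day 183 (6 × 30.44 = 182.6). Later starts are possible, since the everolimus section sets no latest day, but no section names one.
- **The SAP's log-rank test is invalid.** The SAP applies it to survival rates and does not name this composite. The fair statement is only that the test would need a common origin if it were used here.

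The Introduction's remark that GFR changes most in the first 3 to 6 months is thin support. The reference behind it is a cyclosporine study in renal transplantation. The point does not depend on it, because an uncontrolled change is uninterpretable in any case.

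**Conclusion.** The point holds within limits. For the composite, tBPAR on this clock and the eGFR change, the stated rule cannot be applied to 54 of 90 subjects (60%), nor to Group 2 non-starters. As written it yields only single-arm results in at most 36 patients. The objectives affected are secondary-level, and the transplant-dated endpoints are untouched.

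This rests on two readings. The first is that everolimus is assigned to Group 2 only, as the title, the regimens and the Introduction say, despite the sentence about all patients. The second is that these objectives were meant to inform comparisons between arms. If they were meant only as a description of Group 2, the plan should say so.

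**What to change.** In the Efficacy objectives section and the tBPAR definition, replace the start of everolimus by one origin that does not depend on starting it.

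- **Composite and tBPAR:** count from transplant through month 6 in all randomised patients, as randomised, for every between-arm comparison. A POD 30 landmark for Group 2 v Group 1 may be added as a supportive analysis, with events before POD 30 shown by arm.
- **eGFR:** compare arms at the planned week 8, 12, 16 and 24 visits. For Group 2 v Group 1 only, change from the planned week-4 value may be used, whether or not everolimus was started. State the rule for patients who are dead, re-transplanted or on dialysis at week 4 or at the later visit, since eGFR is not interpretable on dialysis.
- **Results timed from the actual first everolimus dose:** label them descriptive for Group 2.
- **Reconcile** the regimen sections (everolimus added by POD 30, Group 2) with the section on introduction and maintenance of everolimus (at the earliest one month, all patients).

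The cost is wording in the Protocol and SAP. No visits are added, because week-4 and later eGFR are planned in all arms and patients who discontinue are already to be followed for the full six months. The SAP's Mann-Whitney test covers eGFR level or change. The downside is that first-month events, before Groups 1 and 2 diverge, slightly dilute that contrast. The supportive landmark analysis addresses this.

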## **Safety objectives**

To evaluate:

- All AE/SAEs with emphasis on viral infections and reactivation (CMV, EBV, HIV, Hepatitis B and Hepatitis C), hematological and metabolic laboratory parameters, gastrointestinal side effects and malignancies.
- Incidence of treatment-related side effects including incidence of new onset diabetes mellitus (NODM), serum/blood lipid panel, neurotoxicity and hypertension.
- Incidence and reason (e.g. AE) for premature discontinuation of study medication, and premature withdrawal from the study.
- Incidence and reason (e.g. AE) for dose interruption and dose adjustment of study medication.

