# Study Synopsis

## TITLE

An single center, open label, randomized, prospective, phase 4 study of induction and maintenance immunosuppression in adult subjects age >18 years undergoing orthotopic liver transplantation (OLT) with basiliximab, delayed dose tacrolimus plus mycophenolate mofetil and standard of care (SOC) corticosteroids (Group 1) versus basiliximab, delayed dose tacrolimus plus mycophenolate mofetil, SOC corticosteroids, with addition of delayed maintenance everolimus at one month post OLT with subsequent mycophenolate mofetil minimization (Group 2) versus standard dose tacrolimus plus mycophenolate mofetil plus SOC corticosteroids (Group 3; control) with a high risk of developing renal dysfunction following OLT or with concomitant renal dysfunction prior to OLT.

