## **SECONDARY ENDPOINTS**

- Mean serum creatinine, eGFR (MDRD) at weeks 1, 2, 4, 8, 12, 16, 20 and 24
- 1, 3 month and 6 month cumulative incidence of acute allograft rejection episodes, steroid resistant rejection episodes, dialysis requirements
- Incidence of death and/or graft failure at 6 months
- Tolerability and side effect profile of the combination drug therapies
- Incidence of infectious complications
- Time to first episode of acute rejection
- Refractory rejection episodes (requiring immunosuppression beyond T cell depletion)
- Rejection episodes per subjects
- Number of subjects requiring full-dose calcineurin inhibitor rescue therapy
- Monitor CD25 cell count for 3 months
- Economic analysis to determine cost-effectiveness of induction therapy with IL-2 monoclonal antibody
- Economic analysis to determine cost-effectiveness of delayed therapy with mTOR

**A three arm, single center, randomized, prospective, pilot trial of induction and maintenance immunosuppression with basiliximab, delayed dose tacrolimus plus mycophenolate mofetil, and SOC corticosteroids versus immunosuppression with basiliximab, delayed dose tacrolimus plus mycophenolate mofetil, and SOC corticosteroids with delayed addition of everolimus and mycophenolate minimization versus standard dose tacrolimus and mycophenolate mofetil plus corticosteroids in patients undergoing orthotopic liver transplantation (OLT) with concomitant renal dysfunction**

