### **Adverse Events**

An adverse event is any adverse change from the patient's pre-treatment condition, which occurs during the course of the clinical trial, whether considered related to the treatment or not. Clinical adverse event will be graded on a 3 point scale (mild, moderate, severe) by the following definitions

1. mild- discomfort noticed, but no disruption of normal daily activity
2. moderate- discomfort sufficient to decrease or affect normal daily activity
3. severe- incapacitating - inability to work or perform normal daily activity

Adverse events will be monitored in the hospital and at clinic visits.

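### One safety objective measures diabetes, neurotoxicity and hypertension as treatment-related effects, with no rule for relatedness, in an open-label trial of three- to five-drug regimens

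*Protocol*

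**What the plan says.** The protocol section Safety objectives has four bullets. The first, which also takes in malignancies, covers "All AE/SAEs with emphasis on viral infections and reactivation (CMV, EBV, HIV, Hepatitis B and Hepatitis C), hematological and metabolic laboratory parameters, gastrointestinal side effects", with no condition on cause. The second is the one at issue: "Incidence of treatment-related side effects including incidence of new onset diabetes mellitus (NODM), serum/blood lipid panel, neurotoxicity and hypertension". The other two concern discontinuation or withdrawal, and dose interruption or adjustment.

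The section Adverse Events defines an adverse event as any adverse change from the pre-treatment condition "which occurs during the course of the clinical trial, whether considered related to the treatment or not". On assessment it says only: "Clinical adverse event will be graded on a 3 point scale (mild, moderate, severe) by the following definitions". That scale measures severity. No causality scale, assessor or reference drug is given.

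The listed secondary endpoint on safety is "Tolerability and side effect profile of the combination drug therapies", again without a condition on relatedness. The SAP gives general tests (Mann-Whitney, chi-square or Fisher's exact, log-rank) and mentions neither adverse events nor attribution.

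The protocol title describes "An single center, open label, randomized, prospective, phase 4 study of induction and maintenance immunosuppression". Group 3 receives "standard dose tacrolimus plus mycophenolate mofetil plus SOC corticosteroids (Group 3; control"), which is three components. Group 1 has basiliximab as well, making four. Group 2 has those four plus everolimus from about one month, making five.

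**The concern.** Read plainly, the second bullet makes relatedness to treatment part of what is counted. Every arm receives tacrolimus, mycophenolate and corticosteroids, so whether a new case of diabetes or hypertension is due to treatment is seldom clear from the event itself. In an open-label trial, whoever decides can know the arm and how many drugs could be blamed. If the decision leans differently by arm, the reported incidence can differ when the true incidence does not, or agree when the true incidence differs.

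This matters for these outcomes in particular because the second bullet is the only place that names three of them. It is therefore the natural source for any table of diabetes, neurotoxicity or hypertension by arm.

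**Working it through.** The documents state no event rate, attribution rate or power for these outcomes, so there is no plan figure to reproduce. The one related figure checks: 90 split 2:2:1 is 90 × 2/5 = 36, 90 × 2/5 = 36 and 90 × 1/5 = 18, as the synopsis states.

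**The text side by side**
- *Collection:* every adverse event, related or not (Adverse Events).
- *Evaluation, first bullet:* all adverse events and serious adverse events, including metabolic laboratory parameters.
- *Evaluation, second bullet:* treatment-related effects, naming diabetes, lipids, neurotoxicity and hypertension.
- *Rule linking collection to the second bullet:* none in either document.

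The unfiltered data are thus already due to be collected. The filter is an extra step with no stated method.

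**What an unequal filter could do (illustration; all rates assumed)**

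Let p be the true incidence and q the probability that an event is called related. The counted incidence is p × q. If p is the same in Groups 2 and 3, the spurious difference is p × (q2 − q3).

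- p = 30%, q2 = 80%, q3 = 40%: 0.30 × 0.80 = 24% v 0.30 × 0.40 = 12%. Expected counts are 36 × 0.24 = 8.6 and 18 × 0.12 = 2.2 patients.
- p = 30%, q2 = 60%, q3 = 40%: 0.30 × 0.60 = 18% v 12%.
- Mirror of the first case, q2 = 40% and q3 = 80%: 12% v 24%. Nothing in the documents prefers one direction.
- A filter can also hide a difference. With true rates of 30% and 20% and q of 60% and 90%, 0.30 × 0.60 = 18% and 0.20 × 0.90 = 18%.

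The effect on the SAP's Fisher test (two-sided, 0.05, 36 v 18) was found by summing the two binomial probabilities over all tables with p < 0.05. With p = 30% in both arms and all events counted, it rejects 3.4% of the time. At 24% v 12% it rejects 12.8%, and at 18% v 12% it rejects 4.8%.

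Over a wider set of assumptions, with equal true incidence of 10% to 40% in both arms:

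| Called related, Group 2 v Group 3 | Spurious difference | Fisher rejection |
|---|---|---|
| All events counted | 0 points | 2.5% to 3.9% |
| 90% v 80% | 1 to 4 points | 1.8% to 4.1% |
| 90% v 70% | 2 to 8 points | 1.4% to 6.1% |
| 90% v 50% | 4 to 16 points | 0.9% to 16.6% |

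Modest gaps in attribution hardly affect the test. Large gaps distort the reported percentages, and at the higher event rates they also raise the false-positive rate.

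**The case against.** The strongest reply is that the safety plan as a whole does not depend on this bullet. The first safety objective takes in all adverse events, and the listed endpoint and the secondary objective on tolerability carry no filter. New diabetes, hypertension and neurological events fall under the adverse event definition in every arm. This stands, and it limits the point to one bullet. A reader might infer that the trial's key safety endpoint counts only related events, but the protocol labels no safety endpoint as key and evaluates all events elsewhere. Nor does the bullet contradict the adverse event definition: collecting everything and describing a subset are compatible.

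Second, treatment-related may be only a class label for expected drug toxicities. The lipid panel, a laboratory measurement that needs no attribution, sits in the same list, which favours that reading. The text does not settle it. No causality step is described, so it is also an inference that investigators would judge relatedness. Deleting the term removes the ambiguity either way.

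Third, a reader might infer that the filter would inflate counts in the everolimus arm. The documents do not support a direction. Of the effects in this bullet, the Introduction names only dyslipidemia as an mTOR class effect. Group 3 has the higher tacrolimus target (5-12 ng/mL, against 4-6 and then 2-5 ng/mL in Group 2), so attribution could lean towards control. Everolimus starts at about one month, so earlier events cannot be ascribed to it.

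Finally, removing the filter does not make ascertainment objective. Diabetes, hypertension and neurotoxicity have no diagnostic definition in either document, and the word neurotoxicity itself implies a cause. This also stands, and the fix has to deal with it.

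**Conclusion.** The point holds in a limited form. One safety objective is worded as related-only incidence, it is the only place that names diabetes, neurotoxicity and hypertension as outcomes, and no assessor or rule for relatedness is given in an open-label trial with unequal regimens. If it is analysed as worded, the arms may not be counted alike. It would go too far to say that they will not be, or to say which arm would look worse.

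The size is unknown. The 24% v 12% example and the 1 to 16 point range rest on assumed incidence and attribution rates, not on the documents. The conclusion assumes that the words mean a filter; if they are only a label, what remains is unclear wording. Either way this is a minor point with a simple remedy.

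**What to change.** - In Safety objectives, delete treatment-related from the second bullet.
- In the SAP, state that the incidence of all new-onset diabetes, neurological adverse events and hypertension will be compared by arm with confidence intervals, regardless of attribution.
- Give an objective definition for each in the SAP, including how pre-existing disease at baseline is handled. Replace neurotoxicity with a named set of neurological adverse events, so that cause is not built into the term.
- Summarise lipids as measured laboratory values by arm and time point. Do not use the cholesterol and triglyceride limits in exclusion criterion 11 as event thresholds: they are baseline eligibility limits, not on-study definitions.
- Show any related-only tabulation as supplementary, and say who judged relatedness and how.

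The cost is one deletion in the protocol and a few lines in the SAP. The events are already to be collected and the lipid profile is already to be monitored. The protocol does not list glucose or blood-pressure measurements by visit, so the definitions should be checked against what is routinely recorded before they are fixed.
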